6.2. Study benefits

The patient could get direct benefit from the study participation in terms of reduction of oesophageal temperature alerts during the procedure and more durable PVI, translating into freedom from AF and no need for redo procedure.

The main benefits will be for future patients if the best combination of RF power and LSI is found for ablation on LA posterior wall.

7. PARTICIPANT IDENTIFICATION

7.1. Study Participants

Patients aged 18-80 years old, scheduled for elective AF ablation in view of a history of symptomatic and drug-refractory AF.

7.2. Inclusion Criteria

The participant must satisfy the following conditions:

- male or female, aged 18 to 80 years;
- willing and able to give informed consent for participation in the study;
- history of symptomatic and drug-refractory atrial fibrillation;
- planned AF ablation on a clinical basis.

7.3. Exclusion Criteria

The participant may not enter the study if ANY of the following apply:

- previous AF ablation;
- pregnancy, trying for a baby or breast feeding;
- oesophageal obstruction (mass, stricture), diverticulum or varices, tracheo-oesophageal fistula or any other oesophageal conditions prohibiting the use of oesophageal temperature probe for continuous luminal temperature monitoring;
- any other significant disease or disorder which, in the opinion of the investigator, may either put the participants at risk because of participation in the study, or may influence the result of the study, or the participant's ability to participate in the study.

8. STUDY PROCEDURES

8.1. Recruitment

Potential participants will first be approached 4-6 weeks before the AF procedure. Outpatient clinic letters of patients placed on the waiting list for catheter ablation of AF by the OUH NHS Trust Cardiac Rhythm Management team will be screened by a member of the research team to assess suitability for inclusion in the study. A letter of invitation, a patient information leaflet and a consent form will be given to potential participants at their routine clinic visits or sent by post at the time their procedure date is determined (usually 6 weeks in advance). The letter will contain a reply slip which patients can use to express their interest in the study and request more information if they wish. The participant will be allowed time to consider the information, and the opportunity to ask questions to the Investigator, their GP or other independent parties to decide whether they will participate in the study.

Once patients have had time to consider the information (and discuss with relatives, friends and their GP if they wish), they will be contacted by an investigator who will ask if they wish to discuss the study further. If they wish to take part, they will be approached at their pre-admission visit before the procedure (1-2 weeks before the AF ablation) for a baseline visit including informed consent, screening and eligibility assessment and randomization.

8.2. Baseline visit

8.2.1. Informed Consent

Informed consent will be obtained by a qualified and experienced investigator who is familiar with the study protocol and procedures. This may be the chief investigator, a principal investigator, the research fellow or a research nurse. The list of eligible individuals will be specified in the delegation log.

Written versions of the Participant Information and Informed Consent will be presented to the participants detailing no less than: the exact nature of the study; what it will involve for the participant; the implications and constraints of the study and the benefits and risks involved in taking part. It will be clearly stated that

the participant is free to withdraw from the study at any time without giving a reason or any prejudice to future care and rights.

Written Informed Consent will then be obtained by means of participant dated signature and dated signature of the person who presented and obtained the Informed Consent. A copy of the signed consent form will be given to the participants. The original signed form will be retained at the study site. The participant must personally sign and date the latest approved version of the informed consent form before any study specific procedures are performed.

8.2.2. Screening and Eligibility Assessment

It will include:

- a. demographics;
- b. exclusion of pregnancy or breast feeding in case of child-bearing age female;
- c. detailed collection of any relevant medical history, but especially concerning AF, heart (including left atrial size and left ventricular function on most recent echocardiogram if any) or oesophageal diseases;
- d. list of current medications and antiarrhythmic drugs previously taken;
- e. current heart rhythm on 12-lead ECG.

8.2.3. Randomisation

A block randomization, with blocks of size four, type 1234, will be used to assign each patient to one of the following four treatment arms:

- ✓ Group 1: 20 W RF power and target LSI = 4 on LA posterior wall;
- ✓ Group 2: 40 W RF power and target LSI = 4 on LA posterior wall;
- ✓ Group 3: 20 W RF power and target LSI = 5 on LA posterior wall;
- ✓ Group 4: 40 W RF power and target LSI = 5 on LA posterior wall.

Briefly, the study population will be divided into 4 blocks of 20 patients. Within each block, every patient will be randomly assigned to 1 of the 4 treatment arms by using sealed envelopes. At the end of each block of 20 patients, there will be 5 patients enrolled in each of the 4 treatment arms. At the baseline visit, following consent, the study nurse or doctor will telephone the Research Office and ask the administrator to open a sealed envelope from the current block of 20 and reveal the allocated treatment arm. The treatment will be unblinded to the investigator and blinded to the patient.

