5. STUDY DESIGN

The PiLOT-AF study is a prospective single-centre randomized observational study aiming at comparing different RF settings during AF ablation on the LA posterior wall, in terms of oesophageal heating, acute and long-term procedure success and procedural complications.

Patients, age 18-80, scheduled for their first RF ablation because of a history of symptomatic and drug-refractory paroxysmal or persistent atrial fibrillation, will be considered for inclusion in the study.

Potential subjects will initially be approached 4-6 weeks before their ablation procedure, in order to give the patients enough time to consider the information, to ask questions to the Investigator, their GP or other independent parties to decide whether they wish to participate in the study or not.

For those interested in participation, a baseline assessment will be arranged to coincide with their standard pre-admission visit, for informed consent, screening and eligibility assessment and randomization.

All AF ablation procedures will be performed in a standard fashion, under general anaesthesia and with continuous oesophageal temperature monitoring using a sinusoidal multi-sensor oesophageal temperature probe (CIRCAtemp). After LA geometry reconstruction using 3-dimensional electroanatomical mapping EnSite Velocity and a multipolar circular mapping catheter St Jude Medical Optima, a CF ablation catheter Endosense TactiCath through a deflectable sheath St Jude Medical Agilis will be used for PVI. Standardized RF settings will be used during ablation on the LA anterior wall as current practice in our centre. Different RF settings will be used on the LA posterior wall, according to randomization group. Duration of RF delivery on the LA posterior wall will be dictated by achievement of target LSI or oesophageal temperature rise $> 39^{\circ}\text{C}$ during ablation. PVI will be achieved and confirmed after 30 minutes waiting time. In case of acute PV reconnection, ablation at sites of breakthrough signals will be performed in order to achieve durable PVI. The occurrence of acute PV reconnection with sites of breakthrough signals on the LA posterior wall will be recorded for each procedure. The total procedure and RF ablation times will be also collected.

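### Section 8.2.3 states two incompatible block lengths, four and 20; staff who track earlier arms could deduce 25% of allocations in advance under the first and about 6% under the second.

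*Combined protocol and SAP*

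**What the plan says.** Section 8.2.3 contains two descriptions of the blocks.

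- The opening sentence: "A block randomization, with blocks of size four, type 1234, will be used to assign each patient" to one of four arms (20 W or 40 W, each with target LSI 4 or 5). The type label is not explained.
- The paragraph below the list of arms: "the study population will be divided into 4 blocks of 20 patients". It continues: "At the end of each block of 20 patients, there will be 5 patients enrolled in each of the 4 treatment arms".

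The operating steps follow. Once consent is given, a nurse or doctor phones the Research Office. The caller is to "ask the administrator to open a sealed envelope from the current block of 20 and reveal the allocated treatment arm". On blinding: "The treatment will be unblinded to the investigator and blinded to the patient".

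Four other places bear on the point.

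- Section 5 describes a "prospective single-centre randomized observational study", so one team sees the whole sequence.
- Section 7.3 ends with an exclusion for "any other significant disease or disorder which, in the opinion of the investigator", may put the participant at risk or affect the study's result or the participant's ability to take part.
- Sections 5 and 8.1 put consent, eligibility assessment and randomisation, in that order, at one baseline visit. Section 8.1 places it one to two weeks before ablation.
- Section 8.7 excludes patients who withdraw before the intervention from the analysis and replaces them. It does not say which envelope a replacement receives.

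**The concern.** Two people preparing envelopes from Section 8.2.3 could produce different lists, and a reader cannot tell which was used. The difference matters because the block length determines how far past allocations reveal the next one. Each arm is disclosed at the baseline call. Section 8.2.1 requires whoever takes consent to be familiar with the protocol, where the block length is printed.

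If the next arm, or just its power level, can be deduced, the decision whether a patient enters is no longer independent of the allocation. The investigator-judged exclusion is one route by which that knowledge could act. The plausible target is risk of AF recurrence, because Section 8.2.2 collects AF history and left atrial size. AF-free survival is a secondary outcome. With 20 patients per arm, a few such decisions could shift baseline risk between arms. Section 11.2 specifies ANOVA and chi-square tests without covariate adjustment, and Section 11.1 intends the results for sizing a main study.

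**Working it through.** **Inputs.** From the protocol: four equal arms, 80 patients, one centre, arms disclosed to staff, block length 4 or 20. Assumed: blocks are permuted at random, and staff know the length and track every earlier arm.

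**The plan's own layout.** 4 blocks × 20 = 80; 20 / 4 arms = 5 per arm per block; 4 × 5 = 20 per arm. Blocks of four give 80 / 4 = 20 blocks with one patient per arm in each, again 20 per arm, and five such blocks give 5 per arm in every 20. The totals therefore cannot show which scheme was meant.

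**The lists are not the same.** Five consecutive permuted fours can be arranged in 24^5 = 7,962,624 ways. A shuffled 20 can be arranged in 20!/(5!)^4 = 11,732,745,024 ways. Only about 0.07% of shuffled twenties would also be five complete fours.

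**Allocations known with certainty.** An allocation is certain when all remaining envelopes in the block hold one arm. With k envelopes per arm and four arms, the expected number of one arm's envelopes lying after all 3k others is k/(3k+1). Summed over arms, this is 4k/(3k+1) per block.

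- Block of 4 (k = 1): 4/4 = 1 per block; 1/4 = 25%; 20 of 80.
- Block of 20 (k = 5): 20/16 = 1.25 per block; 1.25/20 = 6.25%; 5 of 80 on average.
- For comparison, known fixed lengths of 8 and 12: (8/7)/8 = 14.3% and (12/10)/12 = 10.0%.

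**Power level only (20 W or 40 W).** With n envelopes per level, the expected number certain is 2n/(n+1) per block.

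- Block of 4 (n = 2): 4/3 per block; 33.3%; about 27 of 80.
- Block of 20 (n = 10): 20/11 = 1.82 per block; 9.1%; about 7 of 80.

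**Best guess.** Always guess the category with most envelopes left.

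- Arm, block of 4: (1/4 + 1/3 + 1/2 + 1)/4 = 52.1%.
- Arm, block of 20: exact recursion over the remaining counts gives 8.127 correct per block; 8.127/20 = 40.6%.
- Power level: n − 1/2 + 2^(2n−1)/C(2n,n) correct per block. For n = 2: 2.833/4 = 70.8%. For n = 10: 12.338/20 = 61.7%.

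| | Block of 4 | Block of 20 | Simple randomisation |
|---|---|---|---|
| Arm certain | 25% | 6.25% | 0% |
| Arm guessed | 52.1% | 40.6% | 25% |
| Power certain | 33.3% | 9.1% | 0% |
| Power guessed | 70.8% | 61.7% | 50% |

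**Replacements.** The four blocks of 20 contain exactly 80 envelopes. A patient randomised and then replaced under Section 8.7 has used one, so the replacement has no stated source.

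**The case against.** The best defence is that the working procedure is clear. The text names 20 three times, including the instruction on which envelope to open, and four only once. On that reading about 6% of allocations are certain, not 25%. A separate office holds the envelopes and opens them on a telephone request. Deduction would require someone to keep a running record, and the protocol describes none. All of this stands. It narrows the likely size, but the opening sentence remains in force and unreconciled. Five fours nested in each 20 would satisfy both statements, and would bring back the 25%. Remote envelopes do not prevent inference from arms already disclosed.

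Several stronger readings are tempting but lack support.

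- *Eligibility is decided after allocation.* The call is tied only to consent, but Sections 5 and 8.1 and the order of Sections 8.2.1 to 8.2.3 put eligibility before randomisation. What is missing is a check by the Research Office.
- *The exclusion lets staff turn away anyone.* It requires a significant disease or disorder. It involves judgement but is not unlimited.
- *Staff could select on proneness to oesophageal heating, biasing the primary outcome.* Section 8.2.2 lists no measure of oesophageal position, and Section 3.3 says that this position varies and changes over time.
- *Replacements receive the vacated arm.* Section 8.7 does not say so; it is silent.
- *The type label means a fixed repeating order, so every allocation is predictable.* The label is undefined, and the same section says that patients are assigned at random.

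**Conclusion.** The point holds as a contradiction in the allocation rule with a measurable consequence. Certain knowledge covers 20 of 80 allocations (25%) if permuted blocks of four govern, and about 5 of 80 (6%) if envelopes are shuffled within 20. For power level the figures are about 33% and 9%. The second figure of each pair fits the operating text better. All of them are upper limits in one sense: they require staff to know the length and track every earlier arm. The protocol permits this but does not show that it happens.

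A reader might infer that every fourth allocation was known, or that selection took place. The documents support neither. They show an opportunity for selection that the design could remove at almost no cost. The change should be made because the arms are small, the planned comparison is unadjusted, and the results are meant to inform a later trial.

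**What to change.** 1. Remove the block size of four and its type label from Section 8.2.3, and state one scheme for all unopened envelopes. The preferred scheme is randomly mixed block lengths in multiples of four (for example 4, 8 and 12), held only by the Research Office and not printed in the protocol. The minimum is envelopes shuffled within blocks of 20.
2. Require the Research Office to confirm that eligibility assessment is complete, including the investigator-judged exclusion, before it opens the envelope.
3. State that a replacement under Section 8.7 takes the next unopened envelope, with a spare block prepared in advance for when the 80 run out.
4. Record which list was used for patients already randomised. Appendix C shows that at least ten research cases preceded version 1.2.

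The cost is a text amendment and repacking the remaining envelopes, with no extra patients or staff. Interim arm counts may differ by a few patients: within an unfinished block, two arms can differ by up to 3 with a block of 12 (12/4) and up to 5 with a block of 20 (20/4), against 1 with a block of four.

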8.3. AF ablation

The patient will be admitted to hospital on the morning of the procedure or on the night before the procedure, as per local SOP's. Apart from the RF settings on the LA posterior wall that will be dictated by the study randomization group, the AF ablation will be conducted in a completely standard fashion. After the procedure, the patient will be kept in hospital overnight and monitored.

The procedure details are described in the intervention section.

8.4. Pre-discharge review

As part of standard care, each patient will be reviewed the day after the ablation procedure, before discharge. The current symptoms status and occurrence of any procedural complications will be investigated and an ECG will be performed to check the heart rhythm. As part of the research study, the patient will be advised to commence a symptom diary where to record occurrence of palpitations and/or any other cardiovascular symptoms as well as oesophageal symptoms (difficult or painful swallowing, heartburn, acid reflux, sore throat, hoarseness, cough, nausea, vomiting, non-cardiac chest pain).

8.5. Arrhythmia Clinic visit at 3-4 months

As part of standard care, each patient will be reviewed in the Arrhythmia Clinic 3-4 months after the ablation to assess the current symptoms status and check the heart rhythm on ECG. In the case of recurrence of AF, the decision to restart an antiarrhythmic drug and/or to plan a redo procedure will be left to the clinician involved in the care of the patient. Moreover, in accordance with usual practice, additional investigations as prolonged ECG monitoring will also take place dictated by arrhythmia symptoms and assessment for potential adverse events related to the procedure.

8.6. Telephone follow-ups 1 (at 3 months) and 2 (at 6 months)

As part of the research study, telephone follow-ups will be performed 3 and 6 months after the procedure to assess the current symptoms status and collect information about symptoms recorded in the diary. The patient's existing clinical care team will be informed about occurrence of palpitations and any other cardiovascular or oesophageal symptoms and the decision to carry any additional investigations to investigate will be left to them.

8.7. Discontinuation/Withdrawal of Participants from Study

Each participant has the right to withdraw from the study at any time. In addition, the Investigator may discontinue a participant from the study at any time if the Investigator considers it necessary for any reason including:

- Pregnancy
- Ineligibility (either arising during the study or retrospectively having been overlooked at screening)
- Significant protocol deviation
- Significant non-compliance with study requirements
- Withdrawal of Consent
- Loss to follow up

No specific procedures or observations will be required in case of discontinuation/withdrawal of participants from study rather than standard medical care.

The reason for withdrawal will be recorded in the CRF.

In case of withdrawal from the study in an early stage (before the intervention), the patient data will be excluded from the analysis and a new participant will be enrolled.

In case of withdrawal from the study during the follow-up period, neither exclusion of the data of that participant from analysis nor replacement with a new participant will be required.

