- *LA ablation strategy and technique.* The PVs will be encircled in pairs to isolation using an irrigated-tip ablation catheter TactiCath Quartz (SJ Medical, St Paul, MN, USA) via an Agilis deflectable sheath. A point-by-point ablation technique will be used, with a minimum CF of 10 g and a target CF of 20 g for each RF lesion. As current practice, the circumferential ablation line around the PV pairs will be predefined on the electroanatomical LA map, at 1-2 cm from PV ostia with individual adjustments in order to avoid RF delivery in close proximity of the oesophageal probe.

- *RF settings on the LA anterior wall, roof and floor.* As current practice in our centre, an RF power of 40 W will be used on LA anterior wall, roof and floor. The RF application time will be dictated by the achievement of the target FTI and LSI (FTI \geq 400 gs; LSI \geq 6 on LA anterior wall and LSI \geq 5.5 on LA roof and floor).

- *RF settings on the LA posterior wall.* Different RF settings will be used during RF ablation on LA posterior wall, according to randomization group:

- ✓ *Group 1:* 20 W RF power, with target LSI = 4;
- ✓ *Group 2:* 40 W RF power, with target LSI = 4;
- ✓ *Group 3:* 20 W RF power, with and target LSI = 5;
- ✓ *Group 4:* 40 W RF power, with target LSI = 5.

Regardless of the LSI achieved, RF delivery on the LA posterior wall will be promptly terminated in case of any oesophageal temperature rise \geq 39°C or after 60 seconds of continuous RF delivery. The ablation catheter will be then moved to a contiguous lower or higher site on the predefined circumferential ablation line.

- *PVI confirmation.* Disappearance of PV potentials or dissociated PV potentials in the vein and inability to capture the LA during PV pacing will confirm bidirectional block across the PV circumferential ablation line and PVI.

- *Waiting time.* After a waiting time of 30 min, the PVs will be rechecked in order to confirm the persistence of PVI.

- *Acute PVR.* In case of acute PVR, additional RF ablation will be performed in correspondence of breakthrough signals. The same RF settings of the first PV encirclement will be used.

- *Procedure completion.* The procedure will be terminated after achievement of electrical isolation of all PVs. A trans-thoracic echocardiogram will be performed at the end of the procedure to rule out the presence of pericardial effusion. Protamine will be administered to reverse heparin.

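### Section 8.7 lets an investigator who knows the arm end study follow-up after ablation for a deviation, non-compliance or late-found ineligibility, so two 6-month secondary outcomes can go missing avoidably

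*Combined protocol and SAP*

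**What the plan says.** Section 8.7 gives wide discretion: "the Investigator may discontinue a participant from the study at any time if the Investigator considers it necessary for any reason including" is followed by a list that is not exhaustive. The list includes significant protocol deviation, significant non-compliance and "Ineligibility (either arising during the study or retrospectively having been overlooked at screening". None of these is defined further or confined to the time before ablation.

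The same section then says "No specific procedures or observations will be required in case of discontinuation/withdrawal of participants from study", apart from standard medical care. It adds that the reason goes in the CRF, and that data of patients who withdraw during follow-up need be neither excluded nor replaced. Section 11.3 says that data already collected will be analysed unless the patient asks otherwise.

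On blinding, section 8.2.3 states: "The treatment will be unblinded to the investigator and blinded to the patient".

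Section 8.6 describes the 3- and 6-month telephone calls as part of the research study. Section 8.5 describes the 3-4 month Arrhythmia Clinic visit, with ECG, as standard care. Appendix B marks symptom-diary collection at both calls and at the clinic visit. Section 4 lists freedom from AF and oesophageal symptoms over 6 months as secondary outcomes.

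On re-ablation of a reconnected vein, section 9 says "The same RF settings of the first PV encirclement will be used", and the procedure ends only when all veins are isolated.

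**The concern.** Stopping a patient's participation and stopping the collection of that patient's outcomes are different decisions, and section 8.7 treats them as one. For a patient already ablated, the only research contact left is one or two telephone calls. A deviation, non-compliance or an overlooked entry criterion does not make those calls impossible, so the loss is avoidable.

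The decision lies with someone who knows the arm, and one of the grounds may itself depend on the arm. If isolation is hard to reach within certain assigned settings, the operator has more occasion to depart from them, and the documents do not say what follows if isolation cannot be reached within them. If such patients were then discontinued, their 6-month status would be missing for a reason connected with how well the settings worked. Section 11 names no analysis population and no method for missing outcomes that would address this. Section 11.1 says the pilot is meant to inform the design of a main study, so a distorted 6-month estimate could be carried forward.

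**Working it through.** **Arm size.** The plan's figure reproduces. Section 8.2.3 has 4 blocks of 20 with 5 patients per arm in each, so 4 × 5 = 20 per arm and 4 × 20 = 80 in total. Section 11.1 also gives 80. It states no dropout, deviation or discontinuation rate.

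**What is lost, by time of discontinuation** (sections 8.4 to 8.7, Appendix B):
- *Soon after the procedure, for example for a deviation during ablation.* Both research calls lapse. The pre-discharge review and the 3-4 month clinic visit still take place as standard care, but nothing says their findings would be used for the study.
- *After the 3-month call and clinic visit.* Earlier data are kept. The 6-month call lapses, and it is the only scheduled contact after the clinic visit.

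**What is not lost.** Temperature alerts, first-pass isolation, acute reconnection, and procedure and RF times are measured at the index procedure (section 4). Events recorded before discontinuation are kept (sections 8.7 and 11.3).

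**Size without assumed outcome rates.** Each lost patient is 1/20 = 5% of an arm. If m patients are lost, m × 5% of that arm has unknown 6-month status.

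**Illustration 1, all rates assumed.** Suppose the retained patients are 70% AF-free and the m lost patients are AF-free at rate q. The true arm rate is [(20 − m) × 0.70 + m × q]/20, while 70% is observed.
- m = 2, q = 0.50: (12.6 + 1.0)/20 = 68%, an error of 2 points.
- m = 4, q = 0.40: (11.2 + 1.6)/20 = 64%, an error of 6 points.
- m = 6, q = 0.30: (9.8 + 1.8)/20 = 58%, an error of 12 points.

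**Illustration 2, extreme case.** Assume every lost patient had a recurrence not yet recorded. The true rate is taken as 30-50%, borrowed from the repeat-procedure figure in section 3.1, which is not a 6-month recurrence rate.
- Two lost: 6/20 = 30.0% becomes 4/18 = 22.2%; 10/20 = 50.0% becomes 8/18 = 44.4%.
- Three lost: 6/20 becomes 3/17 = 17.6%; 10/20 becomes 7/17 = 41.2%.

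The shifts run from about 6 to 12 points.

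**Illustration 3, symptoms, assumed.** If 4 of 20 patients have symptoms and 2 of them are lost with the symptoms unrecorded, 4/20 = 20% becomes 2/18 = 11%.

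These show how sensitive an arm of 20 is. They do not estimate what will happen in this study.

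**The case against.** A reader might go further and infer that section 8.7 hides the very harms and failures under study. On that reading, a later oesophageal stricture or fistula would meet the exclusion for "oesophageal obstruction (mass, stricture), diverticulum or varices, tracheo-oesophageal fistula or any other oesophageal conditions". A redo, possible because "the decision to restart an antiarrhythmic drug and/or to plan a redo procedure will be left to the clinician", would meet the exclusion "previous AF ablation". The patient could then be removed as newly ineligible. The documents do not support this:

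- The investigator must already know of the injury or redo to act on it. A known event is data already collected, and is kept under sections 8.7 and 11.3.
- Section 7.3 governs entry. Carried forward past treatment, the previous-ablation criterion would exclude every participant at the index procedure. The oesophageal criterion is tied to conditions that rule out the temperature probe, which matters only for the ablation itself.
- Ineligibility arising during the study has an ordinary meaning here. Consent and randomisation take place 1-2 weeks before ablation (section 8.1), and eligibility can change in that interval.

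Three further objections carry weight. The clinic visit with ECG still takes place after discontinuation, and further ECG monitoring may follow if symptoms call for it. No passage says that operators will depart from assigned settings, that this would differ by arm, or that an investigator would end follow-up because of it. And only secondary outcomes of a pilot are exposed, while the pilot's own sizing concerns temperature alerts.

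These points limit the concern without removing it. Keeping data already collected cannot supply a status that was never obtained. Recording the reason documents the loss but does not prevent it. The clinic visit does not reach 6 months.

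**Conclusion.** The point holds as a cheap improvement. Section 8.7 permits avoidable, possibly arm-related loss of freedom from AF and oesophageal symptoms when a treated patient is discontinued for deviation, non-compliance or ineligibility found later. The loss concerns events not yet recorded at that time.

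The documents establish the discretion, the knowledge of the arm and the absence of required study observation afterwards. They do not establish that such discontinuations will happen or will differ between arms. The only size that follows from the plan is 5% of an arm per lost patient. The shifts of 2 to 12 points above depend wholly on assumed numbers lost and assumed outcome rates.

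**What to change.** Amend section 8.7 to separate discontinuation from outcome collection:

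- Once any posterior-wall RF has been delivered, investigator-led grounds (protocol deviation, non-compliance, ineligibility found later) are recorded but do not by themselves end outcome collection.
- These patients keep the symptom diary and receive the 3- and 6-month calls. Their standard-care clinic findings are used, and they are analysed in the assigned arm.
- Outcome collection stops if the patient withdraws consent, is lost to follow-up or dies.
- The statement that no observations are required is limited accordingly.

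Clinical care, and the investigator's discretion over it, stay as they are.

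The cost is one paragraph by amendment and at most two telephone calls per affected patient. Keeping patients with deviations in their assigned arms may dilute a contrast slightly.
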